14.1. Determination of Sample Size

A literature review of similar studies was conducted in order to inform the assumptions for the sample size, for the primary endpoints of $AUC_{0-\infty}$ and C_{max} (see [Table 9](#)).

Table 9. Studies Referenced for Sample Size Assumptions

Program	AUC_{0-t}	$AUC_{0-\infty}$	C_{max}	GIR_{max}	$AUCGIR$	Median	Sample Size
Innovator [NovoLog USPI]		9.8%	25.30%	18.0%	17.6%		24
Mylan (HV) [Hovelmann, 2021]	32.0%	32.0%	30.90%	18.5%	17.5%		71
Sanofi (T1DM) [Kapitza, 2020]	16.0%	15.7%	30.75%	30.8%	30.0%		30
Yichang HEC Changjiang Pharmaceutical Co., Ltd (HV) [Liu, 2021]	17.0%	16.5%	31.0%	22.0%	27.0%		30
Mean	21.7%	18.5%	29.5%	22.3%	23.0%	22.3%	
Median	17.0%	16.1%	30.8%	20.3%	22.3%		

Abbreviation: GIR = glucose infusion rate; HV = healthy volunteers; T1DM = type 1 diabetes mellitus

The CV value ranged from 23.8% to 30.8%, with a mean value of 25.4%. The CV of the Innovator study was 25.3%. Based on the above data, the CV value is selected as 26%.

The sample size is calculated using PASS software with following parameters including 90% power, drop rate 20%, $\alpha=0.05$, 90% confidence interval (CI), assumed actual ratio 0.95 within 80-125%, $N=40$; taking account of 20% dropout, the sample size is determined as $N=54$ to have at least 36 evaluable participants.

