Planned Sample Size	54 healthy male participants are planned to be enrolled in the study to have at least 36 evaluable participants.
Investigational Therapy	NKF-INS(A) administered as a 0.3 U/kg single SC dose in the perumbilical area.
Reference Therapy	EU-NovoRapid® and US-NovoLog®, both administered as a 0.3 U/kg single SC dose in the perumbilical area.

Treatment Duration	The study will consist of a screening period of up to 4 weeks (Days -28 to -1), three treatment periods each consisting of 1-day dose administrations and euglycemic clamp periods (periods 1, 2, and 3) separated by a washout period of 3-14 calendar days between treatment periods 1 and 2, and a washout period of 5-21 calendar days between treatment periods 2 and 3, and a follow-up period of 2-11 days. The entire study duration will be a maximum of 11 weeks.
Pharmacokinetics	Insulin (serum) samples will be collected at 60, 30, 0 minutes pre-dose and 5, 10, 20, 30, 40, 50, 60, 75, 90, 105, 120, 135, 150, 180, 210, 240, 300, 600, and 720 minutes post-dose.
Pharmacodynamics	C-peptide (serum) 60, 30, 0 minutes pre-dose and 5, 10, 20, 30, 40, 50, 60, 75, 90, 105, 120, 135, 150, 180, 210, 240, 300, 600, and 720 minutes post-dose. Blood glucose values will be analyzed pre-dose, every 3 minutes from 0 to 120 minutes, every 5 minutes from 120 to 240 minutes, and every 10 minutes from 240 to 720 minutes post-dose.
Immunogenicity	Not applicable

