Fifty-four healthy male participants are planned to be enrolled in the study to have at least 36 evaluable participants.

The following steps will be taken to minimize variability:

- Prior to each dosing, participants will have been fasting for 10-12 hours
- Individual participants will be dosed at about the same time of day within each treatment period
- The injection site and technique will be standardized between treatment periods
- Any occurrence of a drop in glucose below 3.3 mmol/L will be recorded as this may induce counter-regulatory hormones

The study design schema is provided in [Figure 1](#).

Figure 1. Study Design

Abbreviations: EU = European Union; US = United States

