14.3. Pharmacokinetic Analysis

The primary PK objective is to compare the PK of NKF-INS(A) to US-approved and EU-authorized insulin aspart to demonstrate PK similarity for insulin aspart. The secondary PK objective is to evaluate additional PK parameters of NKF-INS(A) compared to US-approved and EU-authorized insulin aspart. Details on the endpoints are provided in [Table 1](#).

PK concentrations and parameter data will be listed and summarized descriptively (N, arithmetic and geometric mean, SD, CV%, median, minimum, and maximum) by treatment group and graphically.

Biosimilarity between the test product and the US-approved and EU-authorized insulin aspart will be considered separately, i.e., test product vs US-approved product and test product vs EU-authorized product. Biosimilarity of the test and reference products will be assessed on the basis of the 90% Cis for estimates of the geometric mean ratios between the primary PK parameters of the test and reference products in relation to the conventional bioequivalence range of 80% to 125%. The test product will be compared to the reference product by means of statistical analysis with respect to the primary PK parameters using an analysis of variance after logarithmic transformation of the data. Point estimates and 90% Cis for the “test/reference” geometric mean ratios of these parameters will be provided. The primary PK parameters that will be used for the bioequivalence assessment are C_{max} and AUC_{0-t} . All other PK-related assessments of equivalence will be considered secondary.

Any missing samples or non-reportable concentration values will be disregarded in the PK analysis.

Refer to the SAP for full details.

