#### 4.1.1 Sample Size Considerations

A literature review of similar studies was conducted in order to inform the assumptions for the sample size, for the primary endpoints of  $AUC_{0-\infty}$  and  $C_{max}$  (see Table 9 in the NKF-INS(A)-101 CSP; Version 2.0, 6-May-2024).

The CV value ranged from 23.8% to 30.8%, with a mean value of 25.4%. The CV of the Innovator study was 25.3%. Based on the above data, the CV value is selected as 26%.

The sample size was calculated using PASS software [2] with following parameters including 90% power, dropout rate 20%,  $\alpha=0.05$ , 90% confidence interval (CI), assumed actual ratio 0.95 within 80-125%,  $N=40$ ; taking account of 20% dropout, the sample size is determined as  $N=54$  to have at least 36 evaluable participants.

Figure 4.1: Study Design Schematic (from Protocol v2.0, 06-May-2024)

Abbreviations: EU = European Union; US = United States

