### 23.3 Bioequivalence assessment (EU)

As specified in the *Guideline on the investigation of bioequivalence* [3] the test product will be compared to the reference product by means of statistical analysis with respect to the primary PD parameters using an ANOVA with sequence, subject (sequence), treatment and period as fixed effects after logarithmic transformation of the relative PD parameter. Point estimates and 95% confidence intervals (CIs) for the "test/reference" geometric mean ratios of these parameters will be provided.

Biosimilarity will be established on the basis of the 95% CIs for estimates of the geometric ratios between the primary PD parameters of the test and EU-approved reference products are contained within the acceptance range of 80% to 125%. The primary PD parameters that will be used for the bioequivalence assessment are  $\text{GIR}_{\text{max}}$  and  $\text{AUCGIR}_{0-t}$ .

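### The evaluable floor of 36 falls short of the 40 that the plan's own 90% power calculation requires, and the CV of 26% cannot be traced to Table 9, where three of four Cmax CVs are near 31%

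*Protocol*

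**What the plan says.** Protocol 14.1 takes its variability assumption from a literature review summarised in Table 9. It reports: "The CV value ranged from 23.8% to 30.8%, with a mean value of 25.4"%, adds that the innovator study had 25.3%, and concludes: "Based on the above data, the CV value is selected as 26"%. With 90% power, alpha 0.05, a 90% CI, a true ratio of 0.95 and limits of 80-125%, it obtains N=40. It then allows for 20% dropout: "the sample size is determined as $N=54$ to have at least 36 evaluable participants".

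SAP 4.1.1 repeats this and refers to Table 9 as the source: "The CV of the Innovator study was 25.3%. Based on the above data, the CV value is selected as 26"%. The floor of 36 also appears in the synopsis ("54 healthy male participants are planned to be enrolled in the study to have at least 36 evaluable participants") and in protocol 6.1.

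Table 9 gives these Cmax CVs: 25.3% (innovator), 30.9%, 30.75% and 31.0%, with a printed mean of 29.5% and median of 30.8%. Protocol 14.1 names AUC0-∞ and Cmax as the primary endpoints being sized. Protocol 14.3 names Cmax and AUC0-t.

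**The concern.** There are two separate problems.

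- **The floor contradicts the calculation.** The plan computes that 40 evaluable participants are needed for 90% power, then accepts 36 in the same sentence without giving a reason or a power for 36.
- **The CV is not supported by its cited source.** The summary that leads to 26% cannot be recovered from Table 9. For Cmax, a primary parameter that must pass on its own, three of the four tabulated CVs are well above 26%.

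The 90% is the only power figure in either document. As written, 36 evaluable participants could be taken as meeting the design, and a reader would take the Cmax comparison to be better powered than the sponsor's own table suggests. This bears on the chance of a false negative result, not on the validity of a positive one.

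**Working it through.** **Inputs (protocol 14.1).** True ratio 0.95; limits 0.80 and 1.25; 90% CI, i.e. two one-sided tests at 5%; CV 26%; dropout 20%; 54 enrolled; floor 36. Assumption: the CVs are within-subject, as the crossover calculation requires.

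**Method.** On the log scale, σ = √ln(1+CV²) and SE = σ·√(2/n). Power is the probability that the 90% CI lies between ln 0.80 and ln 1.25 when the true log ratio is ln 0.95. It is computed exactly, by integrating over the chi-square distribution of the variance estimate with 2n−4 degrees of freedom (three-period crossover). Using n−2 instead lowers each figure by at most 1 point.

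**Step 1: the plan's N.** At CV 26%, σ = √ln(1.0676) = 0.2558.

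- n = 40: SE = 0.2558 × √(2/40) = 0.0572. The distance to the nearer limit is ln 0.95 − ln 0.80 = 0.1719, or 3.005 SE. Subtracting t = 1.665 leaves 1.340, and Φ(1.340) ≈ 91.0%. The exact value is 90.8% (90.3% with n−2). The smallest n for 90% is 39-40, so N=40 reproduces.
- n = 36: SE = 0.0603; 0.1719/0.0603 = 2.851; less t = 1.668 leaves 1.183, and Φ(1.183) ≈ 88.2%. The exact value is 87.8% (87.2% with n−2).

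**Step 2: dropout.** 40/0.8 = 50, and the next multiple of six sequences is 54. Then 54 × 0.8 = 43.2, so about 43 are expected. A floor of 36 means a loss of 18/54 = 33%, not 20%.

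**Step 3: tracing the CV summary.** The printed column means in Table 9 reproduce: AUC0-t 21.7%, AUC0-∞ 18.5%, Cmax 29.5%, GIRmax 22.3%, AUCGIR 23.0%. All 19 cells average 23.1% and range from 9.8% to 32.0%. The Cmax column ranges from 25.3% to 31.0%. By study, the row means are 17.7, 26.2, 24.7 and 22.7%, and the row medians 17.8, 30.9, 30.0 and 22.0%. Of the quoted figures, 25.3% is the innovator Cmax cell, and 30.8% is both the Cmax median and one GIRmax cell. Neither 23.8% nor 25.4% is a cell or a printed summary. Leaving out the type 1 diabetes study does not lower Cmax: (25.3+30.9+31.0)/3 = 29.1%, median 30.9%.

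**Step 4: power against one reference, one endpoint, 90% CI.**

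| CV | 36 evaluable | 40 | 43 | n for 90% |
|---|---|---|---|---|
| 26% (plan) | 87.8% | 90.8% | 92.5% | 39-40 |
| 29.5% (Cmax mean) | 79.4% | 83.4% | 85.9% | 50-51 |
| 30.8% (Cmax median) | 76.0% | 80.4% | 83.1% | 54-55 |
| 29.1% (Cmax mean, healthy volunteers) | 80.4% | 84.3% | 86.7% | |
| 30.9% (Cmax median, healthy volunteers) | 75.7% | 80.1% | 82.9% | |
| 21.7% (AUC0-t mean) | 95.7% | 97.2% | 97.9% | |

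The largest CV that still gives 90% is 25.0% at 36, 26.4% at 40 and 27.4% at 43. Even the lowest Cmax CV in Table 9, 25.3%, gives only 89.3% at 36.

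**Step 5: if the Table 9 CVs are not within-subject.** If they are total CVs, the within-subject value is lower. Power at 36 / 40 / 43 is then 95.3 / 96.8 / 97.7% at 22%, 91.9 / 94.2 / 95.5% at 24%, and 83.2 / 86.8 / 88.9% at 28%.

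**Step 6: PD parameters at Table 9 means.** At 36 / 40 / 43, with the 95% CI of SAP 23.3 (EU): GIRmax 90.3 / 93.1 / 94.7%, AUCGIR 88.5 / 91.6 / 93.4%. With the 90% CI of SAP 23.4 (US): GIRmax 94.8 / 96.5 / 97.4%, AUCGIR 93.7 / 95.6 / 96.7%. PD does not drive the problem.

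**The case against.** The best defence is that 36 is a minimum, not the expected number. At the planned dropout about 43 are evaluable and power at CV 26% is 92.5%, so the design as enrolled meets its claim. At the floor the shortfall is only 2-3 points. No decision rule is tied to 36. If 36 means completers, others with data on the test product and one reference could still contribute, since the PK parameter set needs only one derived parameter; the power at 36 is then a lower bound.

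On the CV, 30.8% does appear in Table 9. The seven AUC0-t and Cmax cells average 182.95/7 = 26.1%, close to the chosen value. AUC0-t is well powered. The Cmax shortfall depends on the CVs being within-subject, and with all 54 evaluable, power would be 92.3% at CV 29.5% and 90.2% at 30.8%.

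These facts are correct, and they support leaving enrolment at 54. They do not remove the two problems. The plan gives no reason for a floor below its own N and no power for it. The pooled average is not the derivation the plan states, and it would not protect Cmax, which has to pass separately. The within-subject condition limits the Cmax figures only; the gap between 36 and 40 exists at the sponsor's own CV.

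**Conclusion.** The concern holds. At the sponsor's own inputs, 90% power needs 40 evaluable participants, and the accepted floor of 36 gives 87-88%. Two of the figures offered in support of CV 26% have no source in Table 9.

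If the tabulated Cmax CVs (29.5-30.8%) are within-subject, the stated 90% is about 4-7 points too high at 43 evaluable and 11-14 points too high at 36. That part is conditional; the arithmetic on the floor is not. All figures are for one endpoint against one reference, so the chance of passing both PK parameters against both references cannot be higher. Type I error, the equivalence limits and the enrolment of 54 are not in question. This should be corrected, but it does not undermine the design.

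**What to change.** Make the following text changes in protocol 14.1 and SAP 4.1.1, and change the floor in the synopsis and protocol 6.1 as well:

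1. Replace the floor of 36 with at least 40 evaluable participants (43 expected at 20% dropout), or keep 36 and state that it gives about 87-88% power at CV 26%.
2. Give the source of the 23.8-30.8% range and the 25.4% mean, or correct them against Table 9, and state whether the Table 9 CVs are within-subject.
3. Add that, if the Table 9 Cmax CVs (29.5-30.8%) are within-subject, power against one reference is about 80-83% with 40 evaluable participants and 83-86% with 43.

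Two further edits are optional: name AUC0-t instead of AUC0-∞ as the primary exposure parameter in the sample size section, and give PD power at the CI level used for each comparison (95% EU, 90% US).

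No added enrolment is needed. The cost is a less favourable stated power for Cmax (about 80-86% instead of 90%) and, with a floor of 40, less room for loss: 14 of 54 instead of 18.

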## 6.3 Statistical tests

Bioequivalence is assumed if 90% (PK) / 95% (PD) of the test and reference ratio of the primary PK/PD parameters confidence intervals (CIs) fall within the limits of 80%-125%.

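### The stated 90% power covers one PK-type test at CV 26% and N=40; under Table 9's mean CVs, passing all four primaries has lower power: about 61–75% (EU) and 68–78% (US) at 36 evaluable, 74–83% and 79–85% at 43

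*Protocol*

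**What the plan says.** Protocol 14.1 and SAP 4.1.1 describe a literature review that "was conducted in order to inform the assumptions for the sample size, for the primary endpoints of" AUC0-∞ and Cmax. A single variability figure follows: "Based on the above data, the CV value is selected as 26" percent. The protocol then gives the remaining inputs: "The sample size is calculated using PASS software with following parameters including 90% power", alpha 0.05 and "90% confidence interval (CI), assumed actual ratio 0.95 within 80-125" percent. These give N=40, and "taking account of 20% dropout" the plan enrols 54 so as to have at least 36 evaluable.

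The analysis sections ask for more than this:

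- **Primaries.** Protocol Table 1 and SAP 3.1 list four: AUC0-t, Cmax, AUCGIR0-t and GIRmax. AUC0-∞ is secondary (Protocol Table 1, SAP 3.2).
- **Comparisons.** Protocol 14.3 treats similarity separately for each reference: "test product vs US-approved product and test product vs EU-authorized product". Protocol 14.4 does the same for PD.
- **Criterion.** SAP 6.3: "Bioequivalence is assumed if 90% (PK) / 95% (PD) of the test and reference ratio of the primary PK/PD parameters" lie within 80–125%.
- **PD confidence level.** It is 95% in Protocol 14.4 and SAP 6.3 (neither separates EU from US) and in SAP 23.3 (EU). It is 90% in SAP 23.4 (US).
- **CVs.** Table 9 column means are AUC0-t 21.7%, Cmax 29.5%, GIRmax 22.3% and AUCGIR 23.0%. The Cmax median is 30.8%.

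**The concern.** The sizing paragraph gives one power figure, and it matches none of three features of the analysis. Cmax, the most variable parameter, has a Table 9 mean CV above the 26% used. PD against the EU product is judged on a wider interval than the one sized. Four parameters are primary, and the chance that all of them pass is lower than the chance that any one does. In addition, the accepted floor of 36 evaluable is below the 40 that the calculation itself produced.

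At stake is whether the sponsor and ethics reviewers can see how likely the trial is to meet its primary criteria if the product behaves as assumed. Type I error is not affected.

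**Working it through.** **Method.** Power of two one-sided tests on the log scale. s = √ln(1+CV²); SE = s·√(2/n); limits ±ln 1.25 = ±0.2231; true difference ln 0.95 = −0.0513. The result is integrated over the distribution of the variance estimate. Residual df are 2n−4 for the three-period crossover; n−2, the two-period convention, is shown as a check.

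**1. The plan's own figure.** CV 0.26 gives s = √ln(1.0676) = 0.2558. At n=40, SE = 0.2558 × √(2/40) = 0.0572. The distance to the nearer limit is 0.2231 − 0.0513 = 0.1718. Power is 90.3% (df n−2) or 90.8% (df 2n−4), so the stated 90% at N=40 reproduces as one parameter, one reference, 90% CI. For dropout, 40/0.80 = 50, and 54 is the next multiple of six sequences (the documents do not give this reason).

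**2. The same test at the floor of 36.** Power is 87.2–87.8% with a 90% CI, and 78.4–79.7% with a 95% CI.

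**3. Each primary at its Table 9 mean CV** (ratio 0.95, df 2n−4). For Cmax, s = √ln(1+0.295²) = 0.289; at n=36, SE = 0.289 × √(2/36) = 0.068.

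| Parameter (CV) | CI | n=36 | n=40 | n=43 |
|---|---|---|---|---|
| AUC0-t (21.7%) | 90% | 95.7% | 97.2% | 97.9% |
| Cmax (29.5%) | 90% | 79.4% | 83.4% | 85.9% |
| GIRmax (22.3%) | 95% (EU) | 90.3% | 93.1% | 94.7% |
| GIRmax (22.3%) | 90% (US) | 94.8% | 96.5% | 97.4% |
| AUCGIR (23.0%) | 95% (EU) | 88.5% | 91.6% | 93.4% |
| AUCGIR (23.0%) | 90% (US) | 93.7% | 95.6% | 96.7% |

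Here n=43 is 54 × 0.80 = 43.2, rounded down. Joint power cannot exceed the Cmax row, so at this CV no correlation between endpoints restores 90% at 36, 40 or 43. Cmax alone first reaches 90% at n=50.

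**4. All four together.** With independent endpoints at n=36, joint power is the product of the marginals: EU 0.957 × 0.794 × 0.903 × 0.885 = 0.607; US 0.957 × 0.794 × 0.948 × 0.937 = 0.675. The upper ends, and the both-reference column, come from simulating a three-treatment crossover with a shared test arm and a common correlation of 0 to 0.8.

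| Evaluable | EU (PD 95% CI) | US (PD 90% CI) | Both references |
|---|---|---|---|
| 36 | 61–75% | 68–78% | 46–64% |
| 43 | 74–83% | 79–85% | 63–74% |
| 54 (no dropout) | 87–91% | 90–92% | – |

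The ranges are approximate to about one percentage point. The both-reference column applies SAP 23.3 to EU and SAP 23.4 to US. If the 95% level in SAP 6.3 also governed PD against US, the US column would equal the EU column.

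**5. Sensitivity at n=36,** from independence to the ceiling set by the weakest parameter. Table 9 median CVs: EU 65–76%, US 70–76%. The selected 26% for all four: EU 49–80%, US 60–88%.

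**The case against.** The strongest reply is that nothing has been miscalculated. That is right: the stated inputs give the stated N, and the point is what the figure covers. A reader might also infer that the plan promises 90% power for the whole primary objective. It does not; 90% appears only as an input, in a paragraph about AUC0-∞ and Cmax.

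The all-four rule is inferred. SAP 6.3 applies its criterion to the primary PK and PD parameters without allowing one to fail, but no section states a co-primary rule, and PK and PD have separate objectives and acceptance paragraphs. If only the two PK primaries are required, joint power is 76–79% at 36 and 84–86% at 43, still short of 90%.

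Thirty-six is a minimum; at the planned 20% dropout 43 remain. This stands, so both sizes are shown.

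Zero correlation is a bound. AUC0-t and Cmax come from one concentration curve, and the two PD primaries from one GIR curve, so the upper part of each range is more plausible. The documents give no correlations.

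The CVs are uncertain. Table 9 averages four sources without weighting, one of them in type 1 diabetes, and does not say that the CVs are within-subject. With the innovator's 25.3%, Cmax has 89% power at 36 and 94% at 43. However, the other three sources put Cmax near 31%.

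**Conclusion.** The point holds as one of scope and disclosure. The 90% is correct for one 90%-CI test at CV 26% and N=40, and is 87–88% at the accepted floor of 36. It does not describe Cmax at Table 9's mean CV, the PD primaries, the 95% CI for PD against EU, or joint success.

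The sizes rest on ratio 0.95 for every parameter, Table 9 mean CVs taken as within-subject, all four primaries required, and correlation 0 to 0.8. On that basis all-four power is below 90% for either reference at 36 and at 43, and reaches about 90% only with almost no dropout.

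Two stronger readings should be avoided. One is a single range per reference from the EU low end to the US high end: the SAP sets different PD intervals for the two comparisons, so they need separate figures. The other is that a missed parameter would be taken as proof of dissimilarity: no section says how a failed interval would be interpreted.

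**What to change.** Keep N=54. In Protocol 14.1 and SAP 4.1.1:

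- Replace the single 90% with a short table of power for AUC0-t, Cmax, AUCGIR0-t and GIRmax. Give each its own Table 9 CV and the CI level that applies to each reference, at 36 and 43 evaluable.
- Add joint power for EU, for US and for both, over a stated correlation range, and say that the CVs are taken as within-subject.
- Name AUC0-t rather than AUC0-∞ as the primary exposure parameter in the sizing text.
- State whether a claim against a reference requires all four primaries to pass.
- Reconcile the PD confidence level for the US comparison: 95% in SAP 6.3 and Protocol 14.4, 90% in SAP 23.4. Protocol 14 lets the SAP override the protocol, but that does not settle a difference within the SAP.

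This costs one recalculation and some wording, with no extra participants. The downside is that the stated power becomes less favourable.

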14.2. Analysis Populations

The following analysis populations are planned for this study:

Screening Population

All individuals who provide informed consent and provide demographic and/or baseline screening assessments, regardless of the participant's randomization status.

Enrolled Population

The Enrolled Population will include all individuals who sign the ICF.

Safety Population

The Safety Population will include all participants who receive any amount of study treatment. This population will be used for the analysis of safety.

Pharmacokinetic Concentration Population

The PK Concentration Population will include all participants in the Safety Population who received any amount of study treatment and have at least 1 post-baseline reportable PK result.

Pharmacokinetic Parameter Population

The PK Parameter Population will include all participants in the PK Concentration Population who have at least 1 PK parameter derived.

Pharmacodynamic Parameter Population

The PD Parameter Population will include all participants in the Safety Population who have at least 1 PD parameter derived.

